5.9.2.5 Neurological

- Patients on IV steroids may be switched to an equivalent dose of oral corticosteroids (e.g. prednisone) at start of tapering or earlier, once sustained clinical improvement is observed.
- Lower bioavailability of oral corticosteroids should be taken into account when switching to the equivalent dose of oral corticosteroids.

Grade 1: Asymptomatic or mild symptoms; Intervention not indicated

- Continue to monitor the patient

Grade 2: Moderate symptoms; instrumental ADL

- Treat symptoms per local guidelines
- Consider 0.5 to 1.0 mg/kg/day methylprednisolone IV or PO equivalent
- If worsens:
 - Treat as Grade 3-4

Grade 3-4: Severe symptoms; Limiting self-care ADL; Life-threatening

- Obtain neurology consult
- Treat symptoms per local guidelines
- 1.0-2.0 mg/kg/day IV methylprednisolone IV or IV equivalent

- Add prophylactic antibiotics for opportunistic infections
- If improves to Grade 2:
 - Taper steroids over at least 1 month
- If worsens or atypical presentation:
 - Consider IVIG or other immunosuppressive therapies per local guidelines

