5.9.2.6 Pulmonary

- Rule out non-inflammatory causes. If non-inflammatory cause, treat accordingly and continue I-O therapy.
- Evaluate with imaging and pulmonary consultation.
- Patients on IV steroids may be switched to an equivalent dose of oral corticosteroids (e.g. prednisone) at start of tapering or earlier, once sustained clinical improvement is observed.
- Lower bioavailability of oral corticosteroids should be taken into account when switching to the equivalent dose of oral corticosteroids.

Grade 1: Radiographic changes only

- Monitor for symptoms every 2-3 days
- Consider Pulmonary and Infectious Disease (ID) consults

Grade 2: Mild to moderate new symptoms

- Pulmonary and ID consults
- Monitor symptoms daily, consider hospitalization
- 1.0 mg/kg/day methylprednisolone IV or oral equivalent
- Consider bronchoscopy , lung biopsy
- Re-image every 1-3 days
- If improves:
 - When symptoms return to near baseline, taper steroids over at least 1 month and consider prophylactic antibiotics
- If not improving after 2 weeks or worsening:
 - Treat as Grade 3-4

Grade 3-4: Severe new symptoms; New/worsening hypoxia; Life-threatening

- Hospitalize
- Pulmonary and ID consults
- 2-4 mg/kg/day methylprednisolone IV or IV equivalent
- Add prophylactic antibiotics for opportunistic infections
- Consider bronchoscopy, lung biopsy

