Grade 2-3 Creatinine > 1.5x baseline to $\leq 6 \times$ ULN	
 Hold the dose of nivolumab See Section 5.9.2.2 for supportive care. Resume therapy per protocol once the toxicity returns to Grade ≤ 1 and when steroid taper (≥ 1 month*) is complete. (* See exception in Section 6.2.) Discontinue treatment if toxicity lasts for > 6 weeks or unable to initiate steroid taper within a 6 week period. If elevations persist > 7 days or worsen: 
 Treat as Grade 4
Grade 4 Creatinine > 6x ULN	
 Discontinue nivolumab See Section 5.9.2.2 for supportive care.
Gastrointestinal (Diarrhea/ Colitis) Toxicity	
Diarrhea/Colitis Grade 1 Diarrhea: < 4 stools/day over baseline; Colitis: asymptomatic	
 Continue nivolumab. 
 See Section 5.9.2.3 for supportive care. If worsens: 
 Treat as Grade (G) 2 or 3/4
Diarrhea/Colitis Grade 2 Diarrhea: 4-6 stools per day over baseline; IV fluids indicated <24 hours (hrs); not interfering with ADL Colitis: abdominal pain; blood in stool	
 Hold the dose of nivolumab See Section 5.9.2.3 for supportive care. If toxicity resolves to Grade ≤ 1 within 5 days resume therapy with study regimen If persists $> 5-7$ days or recur: 
 Resume study regimen per protocol once the toxicity returns to Grade ≤ 1 and when steroid taper (≥ 1 month*) is complete. (* See exception in Section 6.2.) Discontinue treatment if toxicity lasts for > 6 weeks or unable to initiate steroid taper within a 6 week period. If worsens or persists $> 3-5$ days with oral steroids: 
 Treat as Grade 3-4

Toxicity	Nivolumab Dose Management Guidelines

Diarrhea/Colitis Grade 3-4
 
Diarrhea (G3): ≥7 stools per day over baseline; incontinence; IV fluids ≥24 hrs; interfering with activities of daily living (ADL)
 
Colitis (G3): severe abdominal pain, medical intervention indicated, peritoneal signs
 
G4: life-threatening, perforation
	
 • Discontinue study regimen • See Section 5.9.2.3 for supportive care.
Endocrinopathy	

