Grade 3-4 G3:Severe symptoms; Limiting self-care ADL G4:Life-threatening consequences; urgent intervention indicated	
 Discontinue nivolumab See Section 5.9.2.5 for supportive care.
Pulmonary	
Pulmonary Grade 1 Radiographic changes only	
 Consider holding nivolumab See Section 5.9.2.6 for supportive care.
Pulmonary Grade 2 Mild to moderate new symptoms	
 Hold nivolumab See Section 5.9.2.6 for supportive care. Resume therapy per protocol once the toxicity returns to Grade ≤ 1 and when steroid taper (≥ 1 month*) is complete. (* See exception in Section 6.2.) Discontinue treatment if toxicity lasts for > 6 weeks or unable to initiate steroid taper within a 6 week period. If not improving after 2 weeks or worsening: 
 Treat as Grade 3-4
Pulmonary Grade 3-4 Severe new symptoms; New or worsening hypoxia; Life-threatening	
 Discontinue nivolumab See Section 5.9.2.6 for supportive care.
Skin	
Skin Grade 1-2 Covering $\leq 30\%$ body surface area (BSA) (refer to CTCAE v4.0 for term specific criteria)	
 Continue nivolumab per protocol 
 Note: Subjects who have not experienced a Grade 3 drug-related skin AE may resume treatment in the presence of Grade 2 skin toxicity. See Section 5.9.2.7 for supportive care. If persists $> 1-2$ weeks or recurs: 
 Hold nivolumab Once improving, taper steroids over at least 1 month*, and resume study regimen per protocol. (* See exception in Section 6.2.) If worsens: 
 Treat as Grade 3-4

Toxicity	Nivolumab Dose Management Guidelines
Skin Grade 3 Covering >30% BSA; Life threatening consequences (refer to CTCAE v4.0 for term specific criteria)	
 Hold nivolumab See Section 5.9.2.7 for supportive care. Resume study regimen per protocol once toxicity returns to Grade ≤ 1 and when steroid taper (≥ 1 month*) is complete. (* See exception in Section 6.2.) Discontinue treatment if toxicity lasts for > 6 weeks or unable to initiate steroid taper within a 6 week period.
Skin: Grade 4 (refer to CTCAE v4.0 for term specific criteria)	
 Discontinue nivolumab See Section 5.9.2.7 for supportive care.
Fatigue	

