APPENDIX E: BLOOD SHIPPING GUIDELINES FOR EXTERNAL NON-COH SITES

Follow the requirements for the proper packaging and shipping of biomedical material found in 42 CFR Part 72 - Interstate Shipment of Etiologic Agents Centers for Disease Control and Prevention, Office of Health and Safety Biosafety Branch.

When to ship and temperature of shipment:	BCT tubes: Via overnight courier at ambient temperature . Green-tops: On the day of collection overnight at around +4 °C with a refrigerated cool pack in an appropriate container via FedEx
Days to ship:	Monday-Wednesday for receipt Tuesday-Friday by the laboratory. If this is not feasible, advance arrangements should be made with [name] ([contact]) or [name] ([contact]) or their representative.
Notification on the day of shipment	Email the FedEx shipment # with a copy of Appendix D . 
 • [name] ([contact]) or • [name] ([contact]) or their representative
What to include with the shipment	
 • Copy of Appendix D • Copy of the latest CBC results (with differential) and the date of the test
Shipment address	[name] Analytical Pharmacology Core Facility [name] City of Hope National Medical Center [name] [name]

APPENDIX G: EXPEDITED REPORTING COVERSHEET**NOTIFICATION OF UNANTICIPATED PROBLEM/SERIOUS ADVERSE EVENT****For Use by Participating Institutions Only**

THIS FORM ALONG WITH A COPY OF THE MEDWATCH 3500 OR IRB REPORTING FORM MUST BE **EMAILED TO [contact]** WITHIN 24 HOURS OF KNOWLEDGE OF ONSET OF SERIOUS ADVERSE EVENT OR UNANTICIPATED PROBLEM

COH IRB #16378- Participating Site IRB # _____

From:	Date:
Phone No.:	Email:
Reporting Investigator:	
Event:	
Participant ID:	Institution:
Date Event Met Reporting Criteria (as defined in protocol):	

Type of Report:	 Initial  Follow-up
CTCAE Grade:	 G1/mild  G2/moderate  G3/severe  G4/life threatening  G5
Attribution to nivolumab :	 Unrelated  Unlikely  Possible  Probable  Definite

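### Table 6.2.1 places life-threatening skin reactions on the Grade 3 row, which allows nivolumab to restart, instead of the Grade 4 row, which stops it

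*Combined protocol and SAP*

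**What the plan says.** Table 6.2.1 in Section 6.2 sets nivolumab dosing by type and grade of toxicity. For skin it gives Grades 3 and 4 separate rows with different actions.

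- **Skin Grade 3.** The descriptor is "Covering >30% BSA; Life threatening consequences", followed by "refer to CTCAE v4.0 for term specific criteria". Nivolumab is held, and then: "Resume study regimen per protocol once toxicity returns to Grade ≤ 1 and when steroid taper" is complete. It is stopped only if the toxicity lasts more than 6 weeks or the taper cannot be started within 6 weeks.
- **Skin Grade 4.** There is no clinical descriptor, only the same CTCAE v4.0 pointer. Nivolumab is discontinued.

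Section 6.2 opens by stating that toxicities are graded by CTCAE v4.0. It adds that the management algorithms complement the investigator's medical judgment and do not replace it.

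Section 5.9.2.7 (skin supportive care) uses the same descriptor as the Skin Grade 3 row, but under one combined heading for Grades 3 and 4.

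**The concern.** The only skin row that describes a life-threatening reaction is the one that lets the drug restart. A site that matches a patient to the printed description would reach hold-and-resume. A site that starts from the grade would reach discontinuation. The two instructions are opposite, and they sit in adjacent rows of the table sites use to decide on redosing.

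At stake is re-exposure to nivolumab after a life-threatening skin reaction. Section 6.1.2 lists toxic epidermal necrolysis and Stevens-Johnson syndrome among the rare expected nivolumab reactions, with a footnote that fatal cases have been reported, so the row is not purely theoretical.

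**Working it through.** No arithmetic applies. The check sets side by side every place where the protocol ties life-threatening wording to a toxicity grade. There are eight.

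| Place | Wording | Grade it belongs to |
|---|---|---|
| Table 6.2.1, diarrhea/colitis | "G4: life-threatening, perforation" | Grade 4 |
| Table 6.2.1, neurological | "Life-threatening consequences; urgent intervention indicated" | Grade 4 |
| Appendix G, reporting coversheet | "G4/life threatening" | Grade 4 |
| Section 5.9.2.5, neurological | "Grade 3-4: Severe symptoms; Limiting self-care ADL; Life-threatening" | Grades 3-4 combined |
| Section 5.9.2.6, pulmonary | "Grade 3-4: Severe new symptoms; New/worsening hypoxia; Life-threatening" | Grades 3-4 combined |
| Section 5.9.2.7, skin | same words as the Skin Grade 3 row | Grades 3-4 combined |
| Table 6.2.1, pulmonary | life-threatening listed with severe symptoms and hypoxia | Grades 3-4 combined |
| Table 6.2.1, Skin Grade 3 | "Covering >30% BSA; Life threatening consequences" | Grade 3 alone |

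The count is 3 at Grade 4, 4 combined and 1 at Grade 3 alone (3 + 4 + 1 = 8). Outside the skin rows, the places that separate the two grades agree 3 out of 3 on Grade 4.

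**Does the separation matter elsewhere?** In the colitis and neurological rows, Grades 3 and 4 share one action, discontinuation, so the label changes no decision. In the skin rows the action differs by grade, so it does.

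**Does another row settle it?** The general row for other immune-related events requires discontinuation at Grade 3 or 4. However, it covers only events not specified above it, and its note sends skin events back to the skin rows.

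**Does the six-week limit close the gap?** Not fully. It applies to the duration of toxicity and to the start of the taper. Section 6.2 allows a longer delay for a prolonged taper after consultation with the Study PI.

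**Likely origin (an inference).** The descriptor matches the combined Grade 3-4 skin heading in 5.9.2.7, where it does no harm. It appears to have been left whole on the Grade 3 row when the dosing table split the grades. Consistent with this, the Skin Grade 1-2 row still sends worsening cases to a combined Grade 3-4 category that the table's skin section does not have. The row boundaries are intact in the text, so this does not look like an extraction fault.

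**The case against.** The strongest reply is that the row is chosen by grade, and the grade comes from CTCAE v4.0, not from the italic summary in the cell. Section 6.2 says so, Section 7.1 repeats it for adverse events, and both skin cells point there. On that path a Grade 4 skin reaction reaches the Grade 4 row and nivolumab stops.

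There are further safeguards before any restart:

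- A life-threatening event is serious by the definition in Section 7.1. Under Section 7.8.2 it must be reported to the coordinating center and the Study PI within 24 hours.
- Non-COH sites report on the Appendix G coversheet, where life-threatening is printed as Grade 4. COH sites must state the grade (Section 7.8.4).
- Where steroids are used, restart waits for a taper of at least a month, so the report comes first.
- Section 5.6 removes a participant for unacceptable toxicity, or for a change in condition in the investigator's judgment.

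All of this stands, and it makes a wrongful rechallenge unlikely. It does not remove the conflict, because the cell that points to CTCAE v4.0 also labels life-threatening consequences as Grade 3. CTCAE v4.0 is not reproduced in the protocol, so the reading that life-threatening means Grade 4 rests here on the protocol's own labels.

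A reader might also infer that the frequency bands in Section 6.1 give an expected number of affected patients. They do not measure this defect. The nivolumab bands come from pooled monotherapy data (n = 2578), while this trial gives a combination after transplant. Brentuximab vedotin has its own dosing table (6.2.2). Those two named syndromes are not the same as all life-threatening skin toxicity. An event count would also not be a count of wrongful restarts.

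**Conclusion.** The point holds as a minor internal inconsistency in an operative safety table. Its size is one phrase on one row: the only one of eight graded uses that assigns life-threatening to Grade 3 alone. No rate of harm can be derived from the documents, and none is offered.

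Three stronger readings are not supported.

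- **That the protocol intends rechallenge after life-threatening skin reactions.** The Grade 4 row requires discontinuation, and nothing suggests a deliberate skin-specific exception.
- **That life-threatening is Grade 4 everywhere else.** Four of the other seven uses sit under combined Grade 3-4 labels and do not separate the grades.
- **That the toxicity monitoring rule is distorted.** Section 12.3.3 counts any immune-related event of Grade 3 or higher that is at least possibly attributed to treatment, so such a skin event counts at either grade. Its recovery windows for skin events that are not immune-related do depend on grade, but toxicity is recorded by CTCAE v4.0 (Section 11.1.3), not by this table's descriptor.

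No effect on endpoints, sample size or analysis is claimed. The conclusion assumes that the row boundaries are as printed and that sites may consult the descriptor as well as the grade.

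**What to change.** In Table 6.2.1, delete the words about life-threatening consequences from the Skin Grade 3 row and place them on the Skin Grade 4 row, where the action is to discontinue nivolumab. Keep the body-surface-area criterion on the Grade 3 row and the CTCAE v4.0 pointer on both. Section 5.9.2.7 needs no change, because its descriptor covers Grades 3 and 4 together.

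The cost is one phrase moved between adjacent rows, at the latest with the next amendment. Nothing in the sample size, endpoints or analysis changes.

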Grade 2	Continue nivolumab per protocol
Grade 3	
 Hold study agents Resume study regimen per protocol once toxicity returns to Grade ≤ 2 Discontinue treatment if toxicity lasts for > 6 weeks
Grade 4	Discontinue nivolumab
Amylase or Lipase elevation	
Grade 2	Continue nivolumab per protocol
Lipase or amylase Grade 3 Asymptomatic or not associated with clinical manifestations of pancreatitis	
 Continue nivolumab per protocol Consult the Study PI
Isolated Grade 4 amylase or lipase Asymptomatic or not associated with clinical manifestations of pancreatitis	
 Delay the dose of nivolumab until resolution to < Grade 2 Consult the Study PI If toxicity > 7 days from onset, discontinue therapy.
Lipase or amylase Grade 4 Symptomatic or associated with clinical manifestations of pancreatitis	
 Discontinue nivolumab
Laboratory abnormalities	
NOTE: Follow guidelines above for hematologic, hepatic (ALT, AST, total bilirubin), creatinine or amylase/lipase.	
Grade 2	Continue nivolumab per protocol
Grade 3	
 Delay the dose of nivolumab until resolution to \leq Grade 1 Discontinue treatment if toxicity lasts for > 6 weeks
Grade 4	Discontinue nivolumab if not an isolated Grade 4 event and is associated with clinical sequelae and are not corrected with supplementation/appropriate management within 72 hours of their onset.

Toxicity	Nivolumab Dose Management Guidelines
Immune-related (ir) AEs related to Nivolumab (Other than irAEs specified above)	
Note: See above sections for specific orientation regarding the following ir-related toxicities: eye related toxicities, ALT/AST/total bilirubin, creatinine, diarrhea/colitis, endocrinopathies, neurological, pulmonary, and skin.	
Grade 2	
 Hold nivolumab dose Resume study regimen per protocol once toxicity returns to Grade \leq 1 or baseline and if applicable, when steroid taper (\geq 1 month*) is complete. (* See exception in Section 6.2..) Discontinue treatment if toxicity lasts for $>$ 6 weeks or unable to initiate steroid taper within a 6 week period.
Grade 3 or 4	Discontinue nivolumab
Non-hematologic non-immune related toxicities related to Nivolumab (except fatigue and laboratory abnormalities)	

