Grade 2	If persistent $>$ 3 days despite supportive measures, delay the dose of nivolumab until resolution to \leq Grade 1 or baseline
Grade 3	
 Delay the dose of nivolumab until resolution to \leq Grade 1 or baseline Discontinue if toxicity lasts $>$ 7 days.
Grade 4	Discontinue nivolumab

Table 6.2.2 Dose modifications for brentuximab vedotin associated toxicity

Toxicity	Brentuximab vedotin Dose Management Guidelines
Peripheral Neuropathy	
Grade 1	Continue at same dose level
Grade 2	Reduce dose to 1.2 mg/kg and resume treatment
Grade 3	Withhold until toxicity resolves to \leq Grade 2 or baseline, then resume treatment at 1.2 mg/kg [^] [^] Dose reductions below 1.2 mg/kg are not allowed, and toxicities should be managed with dose delays.
Grade 4	Discontinue brentuximab vedotin
Non-hematologic (except peripheral neuropathy)	
Grade 1	Continue at same dose level
Grade 2	Continue at same dose level
Grade 3	Withhold dose until toxicity is \leq Grade 2 or has returned to baseline, then resume treatment at the same dose level. – Note: Patients who develop Grade 3 or 4 electrolyte laboratory abnormalities may continue study treatment without interruption.
Grade 4	Withhold dose until toxicity is \leq Grade 2 or has returned to baseline, then reduce dose to 1.2 mg/kg and resume treatment, or discontinue at the discretion of the investigator ^{a,b,c} a. Dose reductions below 1.2 mg/kg are not allowed, and toxicities should be managed with dose delays. b. Patients who develop Grade 3 or 4 electrolyte laboratory abnormalities may continue study treatment without interruption. c. Treatment should be discontinued for patients who experience Grade 4 infusion-related reactions. See Section 5.9.2 for supportive care.

Toxicity	Brentuximab vedotin Dose Management Guidelines
Hematologic	
Grades 1-3	Continue at same dose level

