Grade 4	
 Withhold until toxicity resolves to ≤ Grade 2 or baseline, then resume treatment at the same dose level. 
 NOTE: Patients who develop Grade 3 or 4 lymphopenia may continue study treatment without interruption In case of grade 4 neutropenia, growth factor support should be instituted and a repeat blood draw to evaluate the grade of neutropenia should be performed within 3 days. Growth factor support (G-CSF or GM-CSF) should be considered for subsequent cycles. If Grade 4 neutropenia recurs despite growth factor support, consider discontinuation or dose reduction to 1.2 mg/kg.

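### The laboratory rows for nivolumab in Table 6.2.1 give Grade 4 a weaker written instruction than Grade 3, and the electrolyte and lymphopenia notes in Table 6.2.2 do not say which agent they cover

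*Combined protocol and SAP*

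**What the plan says.** Section 6.2 of the protocol sends the reader to Table 6.2.1 for nivolumab and to Table 6.2.2 for BV.

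**Table 6.2.1, laboratory abnormalities.** A note at the head of the block takes some values out of it: "Follow guidelines above for hematologic, hepatic (ALT, AST, total bilirubin), creatinine or amylase/lipase". For what remains:
- Grade 2: nivolumab continues.
- Grade 3: "Delay the dose of nivolumab until resolution to" a value no higher than Grade 1. If the abnormality persists beyond six weeks, discontinuation follows.
- The row for the next grade up reads: "Discontinue nivolumab if not an isolated Grade 4 event and is associated with clinical sequelae". It adds a third condition, that the event remains uncorrected 72 hours after onset. No delay is mentioned.

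The hematologic rows of the same table cover anemia, thrombocytopenia and neutropenia. None covers lymphopenia.

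**Table 6.2.2.** Its title is "Table 6.2.2 Dose modifications for brentuximab vedotin associated toxicity". Under the non-hematologic rows it states, at Grade 3 and again at Grade 4: "Patients who develop Grade 3 or 4 electrolyte laboratory abnormalities may continue study treatment without interruption". Under the hematologic Grade 4 row it states: "Patients who develop Grade 3 or 4 lymphopenia may continue study treatment without interruption".

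**The concern.** A site that finds a Grade 3 sodium or potassium value before dosing has two texts to consult. The nivolumab table tells it to wait. A note in the other table says that study treatment need not be interrupted, and does not name an agent. At Grade 4 the nivolumab table is silent on delay, so the note may be taken to fill the silence. For lymphopenia the nivolumab table says nothing, and the only instruction is the note in the BV table.

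Sites will meet these cases. Section 6.1.2 lists lymphopenia and several electrolyte abnormalities (including hyponatremia, hypokalemia and hypocalcemia) as very common with nivolumab, at any grade. Section 10.0 requires a CBC with differential and a chemistry panel at Day 1 of every cycle. At stake is whether the six sites give or withhold nivolumab by the same rule.

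**Working it through.** No figure in the plan depends on this point, so the check sets the rows side by side.

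**Step 1: which nivolumab rows apply.**
- Electrolytes are not among the values that the note sends elsewhere. The block for other non-hematologic, non-immune toxicity also excludes laboratory abnormalities. Electrolytes therefore stay in the laboratory block.
- Lymphopenia is a blood disorder in Section 6.1.2, so the note sends it to the hematologic rows, and none of them names it.

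**Step 2: compare the tables under both readings of the Table 6.2.2 notes.**

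| Finding | Table 6.2.1 (nivolumab) | Notes mean BV only | Notes mean both agents |
|---|---|---|---|
| Electrolytes, Grade 3 | Delay to Grade 1 or lower; discontinue after more than 6 weeks | Compatible: BV goes on, nivolumab waits | Conflict |
| Electrolytes, Grade 4, not all three conditions met | No delay stated; continuing not stated either | Action for nivolumab on the dosing day is unstated | Note supplies permission to dose |
| Electrolytes, Grade 4, all three conditions met | Discontinue nivolumab | Compatible | Conflict |
| Lymphopenia, Grade 3 or 4 | No row | No nivolumab rule exists | Note is the only nivolumab rule |

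**Step 3: can the notes be read as covering both agents?** Section 11.1.2 counts PFS from the first dose of *study treatment*, and Section 12.3.1 calls the *study treatment* promising if at least 45 of 59 patients are alive and progression-free at 18 months. In both places the phrase means the combination. Where Table 6.2.2 means BV alone it can say so, as in its Grade 4 neuropathy row.

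**Step 4: does attribution separate the tables?** Not fully. The neighbouring blocks of Table 6.2.1 for other immune-related events and for other non-hematologic events are limited to toxicity related to nivolumab. The laboratory block has no such limit, so a Grade 3 sodium value attributed to BV falls under both tables.

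**Step 5: order of the grades within Table 6.2.1.** Grade 3 requires a delay and Grade 4 states none. Adjacent blocks move the other way: fatigue goes from hold at Grade 3 to discontinue at Grade 4, and amylase or lipase elevation without pancreatitis goes from continue to delay. This step does not depend on how Table 6.2.2 is read.

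**Step 6: length of a delay.** Six weeks is 42 days, and 42 / 21 = 2 cycles out of at most 8.

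**The case against.** The strongest reply is that Table 6.2.2 concerns BV only. Its title and column header say so, and Section 6.2 assigns each agent its own table. Within Table 6.2.2, resuming treatment at 1.2 mg/kg can refer only to BV, because Section 5.4.2 fixes nivolumab at 3 mg/kg. The electrolyte notes sit beside instructions to withhold BV and read naturally as exceptions to them. Section 6.2 also lets one agent be held while the other is given. On this reading the Grade 3 electrolyte instructions are compatible.

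This reply stands in part. A reader might infer that the two tables flatly contradict each other, and the title and header do not support that. What remains is an ambiguity of scope, because the notes use the regimen-wide term.

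Three other inferences also go too far:
- **That every Grade 3 laboratory value delays nivolumab.** It does not. Nivolumab continues at Grade 3 anemia, thrombocytopenia and neutropenia, and at Grade 3 amylase or lipase elevation without pancreatitis. Hepatic values and creatinine have their own rows.
- **That lymphopenia falls under the Grade 3 delay and the 6-week limit.** The note sends hematologic values out of that block, so lymphopenia is a missing row, not a conflict.
- **That the delay and the 6-week limit extend to Grade 4.** Both appear in the Grade 3 row only.

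It can also be said that silence at Grade 4 is not permission, since the Grade 2 row says expressly to continue. That is fair. The claim here is only that the written instruction is weaker at the higher grade, and the BV-only reading does not change this.

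**Conclusion.** The point holds as a drafting fault in the dosing instructions, in three parts:
- The Grade 3 and Grade 4 laboratory rows of Table 6.2.1 are out of order on any reading.
- The electrolyte note in Table 6.2.2 can be read as overriding the Grade 3 nivolumab delay, or as filling the Grade 4 silence. This part rests on the regimen-wide use of *study treatment* in Sections 11.1.2 and 12.3.1.
- Table 6.2.1 has no lymphopenia rule.

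The size in patients cannot be stated. Section 6.1.2 gives any-grade frequencies only, and its footnote says that laboratory frequencies count worsening from baseline. The documents give no Grade 3-4 rate from which to derive a count.

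A reader might also infer that the test of 18-month PFS is weakened. The documents do not support this. Every eligible patient with at least one dose is evaluable, delays and single-agent continuation are part of the regimen, and the rule of 45 of 59 does not depend on these tables. Sample size, power and the primary analysis are unchanged. The consequence is possible inconsistency between sites in how nivolumab is given. That merits correction because the instructions apply at each dosing visit and the remedy is cheap.

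**What to change.** Reconcile the passages in Section 6.2:
1. In Table 6.2.2, name the agent or agents covered by the electrolyte notes (Grade 3 and Grade 4) and the lymphopenia note, in place of the general term.
2. In Table 6.2.1, state how electrolyte abnormalities and lymphopenia are handled for nivolumab.
3. In Table 6.2.1, reconcile the Grade 3 and Grade 4 laboratory rows, so that the Grade 4 row says what happens to the nivolumab dose when the conditions for discontinuation are not all met.

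The sponsor decides the clinical action in each case; this review takes no view on which instruction is right. The cost is a wording amendment to two tables and notice to the sites. No statistical section changes.
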